10.5.1.2 Analyses of Secondary Efficacy Endpoint(s)

Analysis of secondary efficacy endpoints will be based on the Full Analysis Set. Hypothesis testing for iPFS, iCRR, and OS subgroup are described in multiple testing procedures in [section 10.5.1.1](#).

iPFS and OS excluding disease stage IVM1c subgroup: The analysis for these endpoints will follow that described for PFS.

ORR, DCR, DRR, iCRR, iORR, iDCR and iDRR: These endpoints will be analyzed as described in [Section 10.1](#). In addition, Logistic regression with the same stratification variables used by the PFS analysis will be used to estimate a p-value and a 95% CI for the treatment odds ratio. A 95% CI for the between-arm difference will be estimated

using Wilson's score method with continuity correction. ([Newcombe 1998](#)) (see code fragment in [Appendix C](#)).

DOR and iDOR: DOR and iDOR among responders will be estimated using the KM method.

BOR categories will be summarized (number and percent) by treatment arm as randomized.

10.5.1.3 Agreement of Blinded Independent Central Review (BICR) and Investigator Reported Endpoints

To assess the agreement of the BICR and the investigator reported endpoints for iPFS and iCRR, two by two tables will be created (iPD vs non-iPD, and iCR vs non-iCR respectively) and the kappa coefficient with the 95% CI will be provided (see code fragment in [Appendix C](#)).

10.5.2 Phase 1b

10.5.2.1 Analyses of Primary Endpoint

Subject incidence of DLT

The subject incidence of DLT will be summarized as a binary variable using the DLT analysis set.

10.5.2.2 Analyses of Secondary Efficacy Endpoint

Analysis of secondary efficacy endpoints will be based on the Phase 1b Safety Analysis Set. Analysis of phase 1b efficacy endpoints will be performed after the last subject has had a chance to be followed for 24 weeks from the initiation of pembrolizumab and at the time of the Phase 3 OS primary analysis. All tumor responses will be assessed by investigator per modified irRC for Phase 1b subjects.

ORR, DCR, and DRR will be summarized with associated exact binomial 95% CI ([Clopper & Pearson 1934](#)).

BOR categories will be summarized (number and percent).

[figure not shown]
DOR, PFS, and OS: KM estimates of DOR among responders, PFS, and OS will be provided.

10.5.3 Analyses of Exploratory Endpoints

10.5.3.1 PD-L1 Induction

[figure not shown]
PD-L1 expression from tumor biopsy tissue samples will be reported as positive or negative. PD-L1 induction (ie, change of PD-L1 expression from negative to positive from paired biopsy samples taken before and after initiating talimogene laherparepvec)

will be tabulated overall and for injected and uninjected lesions. The pairing will be based on lesion number. Should there be multiple biopsies on the same lesion after initiating talimogene laherparepvec, and if there is any positive observation, the post-dose observation for PD-L1 will be considered positive. The analysis will include subjects in the PD-L1 Negative Analysis Set in the Safety Set of **Phase 1b**.

10.5.3.3 iORR, iBOR, iDRR, iDOR, iPFS (response evaluation by investigator using modified irRC-RECIST)

These endpoints will be analyzed in the similar manner to corresponding primary and secondary endpoints assessed by BICR.

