3.1.1 Phase 1b Study Design

Phase 1b is an open-label, multicenter, single-arm study. Talimogene laherparepvec will be administered in combination with pembrolizumab to approximately 20 subjects with previously untreated, unresectable, stage IIIB to IVM1c melanoma to evaluate the safety of talimogene laherparepvec in combination with pembrolizumab. In addition, phase 1b will evaluate potential blood and [REDACTED] that associate with response or resistance to talimogene laherparepvec in combination with pembrolizumab.

Subjects enrolled in phase 1b will receive talimogene laherparepvec 5 weeks before the initiation of pembrolizumab treatment to evaluate changes in the blood and [REDACTED] [REDACTED] in individuals who receive talimogene laherparepvec monotherapy prior to the addition of pembrolizumab. The start of talimogene laherparepvec will be defined as week -5. The start of pembrolizumab will be defined as week 0. When talimogene laherparepvec and pembrolizumab are administered on the same day, talimogene laherparepvec should be administered first, if possible.

Talimogene laherparepvec will be administered as an intralesional injection up to 4 mL of 10^6 PFU/mL at day 1 of week -5 followed by up to 4 mL of 10^8 PFU/mL at day 1 of week -2 (ie, 21 days later [+3 days]), at day 1 of week 0 (\pm 3 days), and every 2 weeks (\pm 3 days) thereafter until disappearance of injectable lesions, CR, confirmed PD per modified immune-related Response Criteria (irRC; [Wolchok et al, 2009](#); [Appendix D](#)), intolerance of study treatment, 24 months from the date of the first dose of pembrolizumab, or end of study, whichever occurs first. Due to the mechanism of action, subjects may experience growth in existing tumors or the appearance of new tumors prior to maximal clinical benefit of talimogene laherparepvec. Therefore, talimogene laherparepvec dosing should continue provided that the subject has no evidence of confirmed PD per modified irRC ([Appendix D](#)) and is able to tolerate the treatment.

Pembrolizumab will be administered at a dose of 200 mg, as an intravenous infusion over approximately 30 minutes every 2 weeks (\pm 3 days) starting at day 1 week 0 (ie, at the time of the third dose of talimogene laherparepvec). Pembrolizumab dosing will continue until confirmed PD per modified irRC, intolerance to treatment, 24 months from the date of the first dose of pembrolizumab, or end of study, whichever occurs first.

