The maximum volume of talimogene laherparepvec or placebo administered at any dose is 4.0 mL for any individual lesion. The maximum dose in any treatment is 4.0 mL. Investigators are encouraged to use the maximum amount whenever lesions' properties allow. Dose reduction for adverse events is not allowed. However, if in the course of administration of talimogene laherparepvec or placebo the subject cannot tolerate the full dose due to an injection-related adverse event such as pain, the total volume given should be recorded, and the reason for intolerance should be documented as an adverse event.

The recommended volume of talimogene laherparepvec or placebo to be injected into the tumor(s) is dependent on the size of the tumor(s) and should be determined according to the injection volume guideline in [Table 2](#).

Table 2. Talimogene Laherparepvec or Placebo Injection Volume Guideline Based on Tumor Size

Tumor Size (longest dimension)	Maximum Injection Volume
> 5.0 cm	4.0 mL
> 2.5 cm to 5.0 cm	2.0 mL
> 1.5 cm to 2.5 cm	1.0 mL
> 0.5 cm to 1.5 cm	0.5 mL
≤ 0.5 cm	0.1 mL

For subjects enrolled in phase 1b: At baseline, if there are ≥ 2 lesions, one lesion (ie, the lesion considered lowest priority for injection) amenable for biopsy should be left uninjected at least until it is biopsied at time of initial PR, confirmed disease progression, or week 24 for subjects with stable disease (SD), whichever comes first.

For subjects randomized to phase 3: At baseline, if there are ≥ 2 lesions, one lesion (ie, the lesion considered lowest priority for injection) amenable for biopsy should be left uninjected at least until it is biopsied at week 5 (see [Section 7.2.2](#)). Aside from leaving one lesion uninjected, all other reasonably injectable lesions (cutaneous, subcutaneous and nodal disease that can be injected with or without ultrasound guidance) should be injected with the maximum dosing volume available on an individual dosing occasion ([Table 2](#)). On each treatment day, prioritization of injections is recommended as follows:

- any tumor that does not correspond to the uninjected lesion reserved for biopsy until week 24 (phase 1b) or week 5 (phase 3)
- any new injectable tumor that has appeared since the last injection
- by tumor size, beginning with the largest tumor
- any previously uninjectable tumor(s) that is now injectable

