2.3 Exploratory

The exploratory objectives are:

Phase 1b:

- To evaluate whether talimogene laherparepvec induces changes in PD-L1 expression by immunohistochemistry (eg, negative to positive) in injected and non-injected lesions after starting talimogene laherparepvec in subjects whose tumors are PD-L1-negative prior to receiving talimogene laherparepvec in phase 1b.

Phase 3:

- iORR, iBOR, iDRR, iDOR, iDCR and iPFS (response evaluation by investigator-assessed modified irRC-RECIST)

- To evaluate the incidence of anti-pembrolizumab antibodies when pembrolizumab is administered in combination with talimogene laherparepvec or placebo.
- To evaluate the pharmacokinetics (PK) of pembrolizumab when administered in combination with talimogene laherparepvec or placebo.
- To evaluate PROs as assessed by the EORTC QLQ-C30 subscales.
- To estimate health state utility (HSU) values using the EuroQoL-5D-3 Level (EQ-5D-3L).

3. Study Overview

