7.4 PD-L1 Negative Analysis Set

The PD-L1 negative analysis set will include all subjects that are PD-L1 negative prior to randomization (phase 3) /first IP dose (phase 1b).

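### The phase 1b PD-L1 induction table has no cut at the first pembrolizumab dose, so its rate cannot be attributed to talimogene laherparepvec alone

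*SAP*

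**What the plan says.** The exploratory objective for phase 1b is "To evaluate whether talimogene laherparepvec induces changes in PD-L1 expression by immunohistochemistry (eg, negative to positive) in injected and non-injected lesions" (SAP 2.3), in subjects whose tumors were PD-L1 negative beforehand. SAP section 1 says the clinical study report will include this analysis, and describes it as PD-L1 change brought about by talimogene laherparepvec.

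The rule is in SAP 10.5.3.1. The outcome is "PD-L1 induction (ie, change of PD-L1 expression from negative to positive from paired biopsy samples taken before and after initiating talimogene laherparepvec"). Also, "The pairing will be based on lesion number". Where a lesion has several biopsies after talimogene laherparepvec has started, "if there is any positive observation, the post-dose observation for PD-L1 will be considered positive". Results are tabulated overall and for injected and uninjected lesions. The visible text sets no time window, no split at the first pembrolizumab dose, and no preference for a particular post-dose biopsy.

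Protocol 3.1.1 starts talimogene laherparepvec at week -5 and pembrolizumab at week 0. It says the lead-in is there to look at changes "in individuals who receive talimogene laherparepvec monotherapy prior to the addition of pembrolizumab". Protocol 2.4 adds that the staggered schedule lets correlative work be done on both sides of the point where the drugs are combined.

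Protocol 6.2.1.1 asks that, when a phase 1b subject has two or more lesions, one be "left uninjected at least until it is biopsied at time of initial PR, confirmed disease progression, or week 24" (the last for stable disease), whichever comes first.

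**The concern.** The schedule creates a clean boundary at week 0, with tissue before it exposed to one drug and tissue after it exposed to two. The analysis rule does not use that boundary. A lesion that is first positive on pembrolizumab enters the table as induced, and the table is then read against an objective that names talimogene laherparepvec as the cause.

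The attribution has a use. Protocol 2.4 cites raised PD-L1 expression after talimogene laherparepvec as part of the argument that it makes pembrolizumab work better by changing the tumor microenvironment. A rate that mixes in tissue taken on pembrolizumab cannot support that step. The injected and uninjected rows may also differ in biopsy timing as well as in injection, because several of the visible biopsy times for the reserved uninjected lesion fall on the combination.

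**Working it through.** The documents state no rate, sample size or error figure for PD-L1 induction, so there is nothing to reproduce. The check sets the rule beside the dosing and biopsy times.

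**Timing.** Inputs: talimogene laherparepvec from week -5 and pembrolizumab from week 0 (Protocol 3.1.1); biopsy times for the reserved lesion (Protocol 6.2.1.1); tumor assessment at week 0 before pembrolizumab, then at week 12 and every 12 weeks (Protocol 7.2.2 and Table 5 footnotes); progression seen after the first pembrolizumab dose to be confirmed at least 4 weeks later (Protocol 3.1.3.1). Weeks from the first talimogene laherparepvec dose equal the study week plus 5.

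| Biopsy | Weeks since first talimogene laherparepvec dose | Weeks since first pembrolizumab dose | Counted by SAP 10.5.3.1? | Free of pembrolizumab? |
|---|---|---|---|---|
| During the run-in | up to 5 | none | yes | yes |
| Initial PR seen at week 0, biopsied before the infusion | 5 | none | yes | yes |
| Initial PR seen at week 12 | 12 + 5 = 17 | 12 | yes | no |
| Confirmed progression first seen on pembrolizumab | more than 4 + 5 = 9 | more than 4 | yes | no |
| Week 24, stable disease | 24 + 5 = 29 | 24 | yes | no |

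All five rows count alike. One on-combination biopsy is enough, so the missing time boundary matters even where a lesion has only one post-dose biopsy and the any-positive rule is idle.

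**Possible size, illustration only.** Suppose a lesion is biopsied once in the run-in (probability p1 of reading positive) and once on the combination (probability p2). With independence assumed, the SAP rule counts 1 - (1 - p1)(1 - p2) as induced, while a run-in rule counts p1. None of these probabilities comes from the documents.

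- p1 = 0.00, p2 = 0.30: SAP rule 1 - 1.00 × 0.70 = 0.30; run-in rule 0.00.
- p1 = 0.20, p2 = 0.40: SAP rule 1 - 0.80 × 0.60 = 0.52; run-in rule 0.20.
- p1 = 0.30, p2 = 0.50: SAP rule 1 - 0.70 × 0.50 = 0.65; run-in rule 0.30.

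A lesion biopsied only on the combination enters at p2 and carries no run-in information.

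**Granularity.** Protocol 2.4 reports 21 treated subjects. If each gave one evaluable lesion, one reclassified lesion would move the rate by 1/21 = 4.8 points. If only ten lesions were evaluable (assumed), it would be 1/10 = 10 points. The number of PD-L1-negative subjects is not given.

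**The case against.** The strongest reply is that the rule matches the objective's wording, which covers the whole time from the start of talimogene laherparepvec and nowhere limits it to monotherapy. Protocol 2.4 also intends correlative studies after the drugs are combined, and the purpose sentence in Protocol 3.1.1 names blood and a redacted item rather than PD-L1. This stands in part. On-combination tissue is legitimately of interest, so the overall table should stay. It does not rescue attribution to one drug.

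A second reply is that much of the relevant text cannot be seen: the phase 1b biopsy schedule, the section between SAP 10.5.3.1 and 10.5.3.3, and the topic of a separate supplemental plan. A timed analysis may exist there. This stands, and it is why the fix allows a cross-reference.

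Three stronger readings are tempting, and the documents do not support them:

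- *The run-in can no longer show the effect of talimogene laherparepvec.* Biopsies dated before week 0 could still be tabulated separately. The limitation is in the planned table.
- *Every visible biopsy time for the reserved lesion falls on the combination.* An initial PR can be recorded at the week 0 assessment, before pembrolizumab.
- *The any-positive rule inflates the rate through repeated biopsies.* With 1 - (1 - p)^k, an assumed 10% per biopsy becomes 19% with two and 27.1% with three. But the reserved lesion has one visible biopsy occasion, and no visible text schedules the same lesion for biopsy both in the run-in and on the combination. Inflation is possible under the rule but not shown.

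Finally, SAP 10.5.3.1 plans no test or contrast between injected and uninjected lesions, so confounding with timing is a caution for the reader and not an error in a planned comparison.

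**Conclusion.** The point holds as a limit on attribution. As written, SAP 10.5.3.1 yields the proportion of lesions positive at any time after talimogene laherparepvec starts, with or without pembrolizumab on board. That proportion does not isolate talimogene laherparepvec, yet the objective and the report description credit the change to it.

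The consequence is small: one exploratory, descriptive phase 1b table, with no alpha attached and no bearing on DLT, PFS or OS. The number of lesions affected is unknown, and the percentages in the working rest on assumed positivity rates and independence. The conclusion itself needs neither. It rests on the visible rule, the week 0 start of pembrolizumab, and the planned biopsies at confirmed progression and week 24. It would fall away if a plan not visible here already separates the two periods.

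**What to change.** In SAP 10.5.3.1, keep the overall table and add a split of post-dose biopsies at the first pembrolizumab dose:

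1. For the statement about talimogene laherparepvec, use biopsies taken after its first dose and before the first pembrolizumab dose.
2. Show biopsies taken on or after the first pembrolizumab dose separately, labeled as on combination.
3. Do not apply the any-positive rule across that boundary.
4. Treat a lesion with no run-in biopsy as not evaluable in the monotherapy table only; it stays in the overall table.

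If a supplemental plan already does this, cite it in SAP 10.5.3.1 instead.

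The cost is a few lines of SAP text and an extra table from dated biopsies already held. The downside is fewer evaluable pairs in the monotherapy table, possibly with few uninjected lesions. Keeping the overall table limits that loss.

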10.5.4 Sensitivity Analyses

[figure not shown]
Sensitivity analyses will be performed for the Phase 3 portion of the study utilizing the Full Analysis Set to assess the robustness of select primary and secondary endpoints as noted below. Primary analysis method for primary efficacy endpoints as well as the secondary efficacy endpoints will be repeated for the Per Protocol Analysis Set to assess the impact of IPDs. All p-values will be descriptive.

10.5.4.1 PFS and iPFS Sensitivity Analyses

The following set of analyses will be used to assess the robustness of the PFS and iPFS primary analysis given the potential for ascertainment or time bias due to skipped or unscheduled tumor assessments, or deaths in the absence of prior radiologic evidence of progression that are remote from the last evaluable tumor assessment, and also to assess the impact of subsequent anti-cancer therapy.

- Stratified log-rank and Cox model analyses will be repeated in which PFS/iPFS times not associated with death in the absence of PD/iPD, that are outside of a + 1 week scheduled assessment window, are moved to the next scheduled post-randomization assessment day on both treatment arms. Times will not be moved if the next scheduled assessment is beyond the date of death or the analysis data cutoff date. This analysis will also be performed moving the same PFS/iPFS times to the closest assessment day.
- Stratified log-rank and Cox model analyses will be repeated in which PFS/iPFS death events that occur more than 13 weeks (12 weeks + 1 week window) after the last evaluable radiologic tumor assessment will be censored at the time of the last evaluable radiologic tumor assessment ([Dodd, 2008](#)).
- A complementary log-log model ([Allison, 1997](#)) will be used to estimate the hazard ratio of talimogene laherparepvec in combination with pembrolizumab compared to pembrolizumab alone adjusting for the randomization stratification factors as well as PD-L1 status at baseline (positive vs not positive). The complementary log-log model is based on a Cox model for continuous time in that the data will be grouped into time intervals. Twelve-week time intervals will be used to match the tumor assessment schedule.
- The impact of subsequent anti-cancer therapy on PFS/iPFS will be assessed by summarizing the incidence by treatment arm of selected anti-cancer therapies with potential PFS/iPFS benefit, the timing of such therapies among subjects that received it, and treatment HR estimates of time to first use among all subjects. Stratified log-rank and Cox model analyses will be repeated in which PFS/iPFS censoring at the last evaluable tumor assessment prior to the start of the first selected anti-cancer therapy.

In the event of inadvertent Suspected Unexpected Serious Adverse Reaction (SUSAR) unblinding, an additional sensitivity analysis for PFS will be performed to assess the potential effect of the unblinding, by removing all event data after the date of the SUSAR unblinding from the analysis.

For the iPFS endpoint, analyses will be repeated if applicable imputing an event at the time of a last overall visit response of iPD that was not confirmed as required per modified irRC-RECIST.

Additionally, to assess the robustness of the PFS and iPFS primary and supportive analyses given the potential for bias related to potential informative censoring, the analyses noted for OS potential censoring in [Section 10.5.4.2](#) will be repeated for PFS and iPFS. Censoring times will be classified as (1) administrative (random) if within 91 days (corresponding to maximum lag time allowable between tumor assessments) of the analysis data cutoff date or otherwise (2) informative.

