
^u Radiographic imaging (CT, PET/CT, or MRI) of the chest, abdomen, and pelvis, and CT or MRI of the brain are required at screening. Tumor assessments must also include all other sites of disease. The screening scans must be done within 28 days prior to enrollment. During treatment, radiographic imaging (CT or MRI) of the abdomen, pelvis, and chest, along with tumor assessments of all other sites of disease, (and CT or MRI of the brain if a subject has symptoms or signs suggestive of CNS metastases), will be performed independent of treatment cycle at week 12 (+1 week), and then every 12 weeks (+1 week) or more frequently if clinically indicated until confirmed iPD per modified irRC-RECIST ([Appendix F](#)) or start of new anticancer treatment. Imaging should not be adjusted for cycle initiation delays and performed according to the calendar. The imaging modality selected (eg, CT or MRI) should remain constant for any individual subject. Response or progression should be confirmed by repeated radiographic imaging ≥ 4 weeks after the first indication of response or progression. Radiographic imaging is required at the safety follow up visit if the subject ended treatment prior to confirmed iPD and has not had radiographic tumor imaging performed within 4 weeks (+1 week) of the visit. For subjects who discontinued treatment for any reason other than confirmed iPD, every effort should be made to complete radiographic assessments every 12 weeks (+1 week) or more frequently if clinically indicated during the long-term follow-up until documentation of confirmed iPD per modified irRC-RECIST ([Appendix F](#)), start of new anticancer therapy, or end of study whichever occurs first. The radiographic images will be collected for review of tumor response by a blinded independent central review committee.

^v Response (iCR, or iPR) or iPD to be confirmed by second consecutive response assessment no less than 4 weeks from the date of the first documented response or PD.

Approved

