Measurable tumor burden is defined as the sum of the diameters (longest for non-nodal lesions, short axis for nodal lesions) for all target lesions and up to 10 (maximum 5 per organ) new measurable lesions. The measurable tumor burden will be censored at the start of the first subsequent anticancer therapy, or at the time of complete or partial removal/reduction of any target lesion which contained melanoma on pathology evaluation or pathology results were unknown, whichever occurs first.

Depth of Response (DpR)

DpR is defined based on the maximum post-baseline measurable tumor burden decrease from baseline measurable tumor burden where maximum post baseline-measurable tumor burden decrease is categorized as: G0 = no shrinkage or increase, G1 = $>0 \leq 25\%$, G2 = $>25-50\%$, G3 = $>50-75\%$, G4 = $>75- < 100\%$, and G5 = 100%.

End of Study

Primary Completion: The primary completion date is defined as the date when the last subject is assessed or receives an intervention for the purposes of final collection of data for the primary endpoint(s).. The primary completion date is the date when data for the primary endpoints are last collected for the purpose of conducting the primary analysis.

If the study concludes prior to the primary completion date originally planned in the protocol (ie, early termination of the study), then the primary completion will be the date when the last subject is assessed or receives an intervention for evaluation in the study (ie, last subject last visit).

End of Study: The end of study date is defined as the date when the last subject across all sites is assessed or receives an intervention for evaluation in the study (ie, last subject last visit), following any additional parts in the study (eg, long term follow-up), as applicable.

Evaluable tumor assessment

An overall visit response other than iUE or UE.

Event of Interest (EOI) and Events of Clinical Interest (ECI)

EOIs are defined in version-controlled search strategies maintained by Global Regulatory Affairs and Safety (GRAAS) at Amgen for talimogene laherparepvec and those for ECIs for pembrolizumab will be provided by Merck before the analysis.

Investigational product (IP)

Investigational product (IP) refers to talimogene laherparepvec/placebo (also known as “Amgen IP”) and Pembrolizumab (also known as “non-Amgen IP”) in this study. IP is also referred as study drug, or study therapy.

Last date known to be alive

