Progression-free survival (PFS) per modified RECIST 1.1 (Phase 3)

PFS per modified RECIST 1.1 is defined as the interval from randomization to the earlier event of PD per modified RECIST 1.1 or death from any cause. Subjects without an event will be censored at their last evaluable tumor assessment **if available; otherwise will be censored on randomization date.**

Safety follow-up visit

Safety follow-up visit will be performed approximately 30 (+7) days after the last dose of IP. In addition, serious adverse events will be reported that occur through 90 (+7) days after the cessation of all study treatment or 30 (+7) days following cessation of treatment if the subject initiates new anticancer therapy, whichever is earlier.

Serious adverse events (SAE)

Serious adverse events (SAE) are defined as any adverse event categorized as serious as determined by investigator per protocol defined criteria.

Study day

For phase 3, study day is calculated from the first day IP is administered (ie, non-zero dosing) to the subject. Study day = visit date – first dose date +1 if visit date is on or after the first dose date. Study day = visit date – first dose date, if visit date is before the first dose date.

For phase 1b, study day is calculated from the first day pembrolizumab is administered (ie, non-zero dosing) to the subject. Study day = visit date – first pembrolizumab dose date +1 if visit date is on or after the first dose date. Study day = visit date – first pembrolizumab dose date, if visit date is before the first dose date.

Study Week 0

For phase 3, the start of IP administration (ie, non-zero dosing) to the subject is study week 0. Study day 1 is corresponding to study week 0.

For phase 1b, the start of pembrolizumab is study week 0. Study day 1 is corresponding to study week 0.

Study Week -5

In phase 1b, the start of talimogene laherparepvec is study week -5.

Treatment period

[figure not shown]
Treatment period is defined as the period between the first date of study therapy administration and 30 days after the last study therapy administration.

[figure not shown]
Treatment-emergent Adverse Events (TEAE)

[figure not shown]

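### SAP 10.5.4.1: as worded, the off-schedule-scan sensitivity analysis for PFS and iPFS also moves censoring times forward, by up to about 11 weeks past the last evaluable scan

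*SAP*

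**What the plan says.** SAP 10.5.4.1 introduces its analyses as checks on timing bias from skipped or unscheduled scans. In the first bullet, "PFS/iPFS times not associated with death in the absence of PD/iPD, that are outside of a + 1 week scheduled assessment window, are moved". The direction is forward, since the bullet sends these times "to the next scheduled post-randomization assessment day on both treatment arms". There are two guards: "Times will not be moved if the next scheduled assessment is beyond the date of death or the analysis data cutoff date". A second version follows: "This analysis will also be performed moving the same PFS/iPFS times to the closest assessment day".

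The endpoint definitions are in SAP Section 6. For PFS and iPFS, "Subjects without an event will be censored at their last evaluable tumor assessment", or, where there is none, "otherwise will be censored on randomization date". An evaluable assessment is "An overall visit response other than iUE or UE".

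Protocol Table 6, footnote u, schedules imaging at week 12 and every 12 weeks after that, each with a +1 week window. It allows extra scans when clinically indicated and asks for confirmatory imaging at least 4 weeks after a first response or progression. It adds: "Radiographic imaging is required at the safety follow up visit if the subject ended treatment prior to confirmed iPD", provided no scan was done within 4 (+1) weeks of that visit. SAP 10.5.4 makes all sensitivity p-values descriptive.

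**The concern.** A PFS time is one of three things: a progression, a death without progression, or a censoring time. The bullet exempts only the second. A censored subject whose last evaluable scan fell outside a window is therefore carried forward to a scheduled day. By the SAP's own definition of censoring, no evaluable scan exists between the two dates, so the added progression-free time was not observed.

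The bullet also moves off-schedule progressions to the same scheduled days. A censored time tied with events counts in the risk set, so the moved subjects enlarge the denominator on the days where events have been placed, and they bring no events. If one arm has more such subjects, its hazard is understated. An analysis meant to test for bias from uneven assessment patterns would then add some of its own when those patterns differ between arms.

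**Working it through.** **1. Which times are moved.** SAP 8.1.4 (items 2 and 3) speaks of PFS and iPFS times being censored, so the SAP's use of the word covers censored values. The second bullet of 10.5.4.1 refers to death events where only events are meant. None of the code fragments shown in Appendix C narrows the rule.

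**2. The plan's own figure.** 12 weeks + 1 week = 13 weeks, and 13 × 7 = 91 days. This agrees with the 13 weeks in the second bullet and the 91 days at the end of 10.5.4.1.

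**3. Size of the shift.** Scheduled days are 84, 168, 252 and so on, each with a 7-day window.
- First off-window day after the first scan: 84 + 7 + 1 = 92. Shift: 168 − 92 = 76 days = 10.9 weeks.
- Range 1 to 76 days. If off-window scans are spread evenly, the mean is (1 + 76)/2 = 38.5 days = 5.5 weeks.
- Last scan at week 16: moved to week 24, 8 weeks credited.
- Censored at randomization, read literally: moved to day 84, 12 weeks credited.
- Closest-day version, after the first scan: the midpoint is day 126, so day 127 moves forward 168 − 127 = 41 days (5.9 weeks) at most. Earlier days move backward.

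**4. Whose times are moved.** A subject censored for PFS has no recorded death, so only the cutoff guard can stop the move. That guard leaves recent administrative censoring in place. What moves is mainly the censoring of subjects whose scans stopped early: withdrawal, new therapy, or iPD confirmed by the investigator (which ends imaging) but not called PD by central review.

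**5. Effect on the hazard ratio (HR).** All simulations use the control PFS curve in Protocol 10.2.2 (0.95, 0.60, 0.49, 0.39, 0.32 and 0.30 at 1.5, 3, 6, 12, 18 and 24 months) and 12-week scans. Off-schedule rates and unequal dropout are assumptions; Protocol 10.2.2 gives a single PFS loss rate of 10% per year.
- A: true HR 0.67, 330 per arm, 26-month accrual, 48-month cutoff, 30% chance of an unscheduled scan per interval, 100 runs.
- B: true HR 1, 6,000 per arm, 60 runs, 30% of PDs off schedule; 50% (25% dropout) or 70% (40% dropout) of dropouts' last scans off schedule, some before week 12; Monte Carlo SE about 0.003.
- C: true HR 1, 60,000 per arm, 10 runs, 30% of PDs and half of last scans off schedule; the last scan may itself show PD.

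| Set-up | Dropout per year, treated vs control | HR as written | HR, only PD moved | Relative change |
|---|---|---|---|---|
| A | 10% vs 10% | 0.6760 | 0.6762 | under 0.1% |
| A | 25% vs 10% | 0.6734 | 0.6774 | −0.0040/0.6774 = −0.6% |
| A | 10% vs 25% | 0.6905 | 0.6870 | +0.0035/0.6870 = +0.5% |
| B | 25% vs 10% | 0.983 | 1.003 | −0.020/1.003 = −2.0% |
| B | 40% vs 10% | 0.942 | 1.004 | −0.062/1.004 = −6.2% |
| C | 25% vs 10% | 0.988 | 1.009 | −0.021/1.009 = −2.1% |
| C | 40% vs 10% | 0.976 | 1.024 | −0.048/1.024 = −4.7% |

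In A, including a run of the equal-dropout case with 15% unscheduled scans, about 23 to 48 of 660 subjects had a censoring time moved, by 9 to 10 weeks each on average. The largest single-run difference between the two rules was 0.008. In C, the analysis with no times moved gave 1.009 and 1.023, so moving PD times only returns to the unmoved result rather than to 1.

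**The case against.** The authors may have meant progression times only; the bullet never mentions censoring. Every sizeable effect above needs an imbalance that the documents do not predict. The trial is double-blind with one scan schedule for both arms, and the planned loss rate is a single 10% per year. Stopping for toxicity does not by itself make the safety-visit scan the last one, because footnote u asks for 12-weekly imaging to continue after any stop other than confirmed iPD. The p-values are descriptive, the closest-day version limits the forward shift after the first scan, and 10.5.4.1 examines informative censoring separately.

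Most of this stands, and it limits the point to a wording correction in a supporting analysis. It does not settle the point. If only progressions were meant, the text still has to say so before programming. Withdrawal, new therapy and investigator-confirmed iPD can still end imaging off schedule. Equal dropout is also the case in which this check is least needed.

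A reader might infer that the rule contradicts the endpoint definition in SAP Section 6. That goes too far: a sensitivity analysis may depart from the primary definition, and other bullets in 10.5.4.1 do. The complementary log-log code in Appendix C.18 likewise carries a censored subject through the whole 12-week interval.

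A reader might also fault the death guard, since whether an off-schedule PD is moved depends on later survival. The SAP simply keeps the observed PD date in that case. In a simulation with 12,000 per arm the guard changed the HR by no more than 0.1%, so no change is warranted.

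**Conclusion.** The point holds as a defect of wording with a conditional effect. Read literally, the first bullet of 10.5.4.1 carries off-window censoring times forward by up to 76 days between scheduled scans, or 12 weeks from randomization. With equal dropout the effect on the HR is under 0.001. With more early, off-schedule censoring in one arm, the HR is biased in that arm's favour. The range is about 0.5% to 6%, under assumed dropout of 25% or 40% against 10% per year and the off-schedule rates listed above. The documents give no observed rates, so the range shows sensitivity and is not a forecast.

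Two stronger conclusions are not supported. A reader might infer that the primary PFS result or the alpha-controlled iPFS test is affected; neither is, because the rule appears only in a descriptive sensitivity analysis. A reader might also infer that restricting the rule yields an unbiased HR. It takes away what the move adds, but set-up C shows that bias already in the unmoved analysis remains.

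**What to change.** In the first bullet of SAP 10.5.4.1, state that only PD/iPD event times outside the window are moved and that censored times stay at the last evaluable assessment (or at randomization where there is none). Say that this applies to both the next-scheduled and the closest-day versions. Leave the death and cutoff guards as they are. The cost is one sentence and a small programming condition; no new data are needed.
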